11.6. Prior and Concomitant Medications

Prior and concomitant medication will be coded using the World Health Organization Drug Dictionary (WHO Drug) version September 1, 2014, and will be summarized by drug class and generic name. In addition, prior treatment concomitant medications will be listed.

11.7. Physical Examination and Vital Signs

All vital signs (weight, systolic blood pressure, diastolic blood pressure, heart rate, respiratory rate and body temperature) will be graded according to FDA guidance Toxicity Grading Scale for Healthy Adult and Adolescent Volunteers Enrolled in Preventive Vaccine Clinical Trials and summarized descriptively by infusion rate and time points. The vital signs data will also be listed with any values that lie outside the normal range or are clinically significant will be flagged.

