3. SUMMARY OF STUDY DESIGN

This is a pivotal Phase 3, open-label, single-arm, multinational, multi-center study to assess the tolerability, safety, efficacy, and pharmacokinetics (PK) of Prometic Immune Globulin Intravenous (Human) 10%, the investigational medicinal product (IMP), in adults and children with primary immunodeficiency diseases (PID).

A total of approximately 75 eligible subjects aged 2 to 80 years will be enrolled. Cohort 1 (adults) will enroll approximately 50 subjects aged 17 to 80. Cohort 2 (children) will enroll approximately 25 subjects aged 2 to <17.

- Up to 6 subjects aged 2 to <6 years,
- At least 6 subjects aged 6 to <12 years, and
- At least 6 subjects aged 12 to <17 years.

Only subjects 18 years of age and older and treated with commercially licensed immune globulin product will be enrolled by Russian sites, in accordance with Russian national legislation.

A subset of subjects will be asked to participate in a PK sub-study. Subjects who consent to participate in the PK sub-study will undergo a series of blood draws to assess the PK profile of the IMP before and after Infusion 6 (21-day cycle subjects) or Infusion 5 (28-day cycle subjects).

To enhance subject safety, IMP will initially be given only to adults aged 18-80 years treated with a stable dose of immune globulin, with the timing of the first IMP infusion at staggered intervals. The study will proceed only after evaluation and FDA review of safety data obtained at Week 4 (or Week 3 for subjects on a 3-week treatment regimen) after the first IMP infusion in 15 subjects. The procedures will be as follows:

- **Group 1:** The timing of the first IMP infusion in the first 5 subjects will be staggered at 2-week intervals. Before further subjects receive IMP, the results from these 5 subjects will be evaluated by the Investigators and the Data Safety Monitoring Board (DSMB) and submitted to the FDA for review.
- **Group 2:** Contingent on FDA and DSMB approval after review of the interim safety results in Group 1, 10 further subjects will receive the first IMP infusion staggered at an interval to be determined by the FDA after review of the Group 1 results. Before further subjects receive IMP, the results will be evaluated by the Investigators and the DSMB and submitted to the FDA for review.

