11.5.5. Safety Laboratory Data

Safety laboratory parameters will be graded according to FDA guidance Toxicity Grading Scale for Healthy Adult and Adolescent Volunteers Enrolled in Preventive Vaccine Clinical Trials and summarized using descriptive statistics at baseline and at each subsequent time points. Those lab parameters that are not defined in the FDA guidance will be summarized descriptively.

All laboratory results will be tabulated for the safety population.

All laboratory results will be provided as a listing, and any values that lie outside the normal range or are clinically significant will be flagged.

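### The SAP grades laboratory values and vital signs of all ages on a scale titled for healthy adults and adolescents, so grades for children aged 2 to <12 may be invalid

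*SAP*

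**What the plan says.** SAP 11.7 makes no exception for age or for any individual sign: "All vital signs (weight, systolic blood pressure, diastolic blood pressure, heart rate, respiratory rate and body temperature) will be graded". Weight is in that list. The values are to be "graded according to FDA guidance Toxicity Grading Scale for Healthy Adult and Adolescent Volunteers Enrolled in Preventive Vaccine Clinical Trials".

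SAP 11.5.5 adopts the same scale for the laboratory: "Safety laboratory parameters will be graded according to FDA guidance Toxicity Grading Scale for Healthy Adult and Adolescent Volunteers". It has one fallback: "Those lab parameters that are not defined in the FDA guidance will be summarized descriptively". It then sets the population: "All laboratory results will be tabulated for the safety population". SAP 5.2 defines that population as every enrolled subject who received IMP or commercial product, so children are in it.

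On age, SAP 3 says: "Cohort 2 (children) will enroll approximately 25 subjects aged 2 to <17". The strata are "Up to 6 subjects aged 2 to <6 years", "At least 6 subjects aged 6 to <12 years", and a minimum of 6 aged 12 to <17. SAP 6.1 asks for descriptive results by cohort and for each age group within Cohort 2.

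Both SAP sections also provide listings in which values beyond the normal range, or judged clinically significant, are flagged.

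**The concern.** A grading scale carries fixed thresholds for the people it was written for. By its title, this one was written for adults and adolescents, and the SAP applies it to children as young as 2 without a pediatric alternative. Because SAP 6.1 reports the age groups separately, the graded tables for ages 2 to <6 and 6 to <12 would consist entirely of children outside the titled age range.

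At stake is how the pediatric safety tables are read. Protocol 12.5 intends the Cohort 2 data to support a BLA for the pediatric population. A grade that does not mean the same thing in a 4-year-old as in an adult is weak evidence of either safety or harm. The tables would also show grades visit by visit without saying what had changed since baseline.

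**Working it through.** The plan gives no figure on this point, so there is none to reproduce. The check sets the texts side by side and then bounds how many children are involved.

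**1. Scale against population.**

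| Item | Source | Content |
|---|---|---|
| Scale's titled population | SAP 11.5.5, 11.7 | Healthy adults and adolescents in vaccine trials |
| Age limit on its use | SAP 11.5.5, 11.7 | None |
| Pediatric scale or age-specific range | SAP 11.5.5, 11.7 | None named |
| Laboratory fallback | SAP 11.5.5 | Depends on whether the scale defines the parameter, not on age |
| Vital-sign fallback | SAP 11.7 | None |
| Normal-range flags | SAP 11.5.5, 11.7 | Planned in listings; not stated to be age-specific |
| Youngest subjects | SAP 3 | Age 2 |

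The mismatch is therefore a stated rule that reaches subjects outside the scale's title. The laboratory fallback does not cover it.

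**2. How many children.** Let a, b and c be the numbers aged 2 to <6, 6 to <12 and 12 to <17. SAP 3 gives 0 ≤ a ≤ 6, b ≥ 6, c ≥ 6 and a + b + c ≈ 25. Neither document defines adolescence; I take it to start at 12. The number below the scale's titled range is a + b = 25 − c.

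- Minimum: a = 0, b = 6, so a + b = 6 (c = 19). 6/25 = 24%.
- Maximum: c = 6, so a + b = 25 − 6 = 19. 19/25 = 76%.
- If the youngest stratum fills (a = 6): the minimum is 6 + 6 = 12 and the maximum stays at 19.
- As a share of all 75 subjects: 6/75 = 8% to 19/75 = 25%.

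The other 6 to 19 children, aged 12 to <17, fit the title by age.

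**3. How many values would be misgraded.** This needs the scale's cut-offs and age-specific ranges. Neither is in the documents, so no rate or range can be given.

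**4. Does the protocol itself adapt criteria for children?** Protocol 21.1 recommends age-specific pediatric sepsis criteria. It gives leukocytosis as WBC above 12,000/mm³ under bacteremia/sepsis, but in its pediatric pneumonia remarks it cites counts above 15,000/mm³ or below 5,000/mm³. Those passages concern diagnosing infection, not grading toxicity. They show only that the protocol's own appendix does not carry adult criteria over to children unadjusted.

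**5. Change from baseline.** Protocol 5.2 lists changes from baseline in laboratory parameters, and vital sign changes, among the safety endpoints. SAP 11.5.5 plans grades and descriptive statistics at baseline and each later time point. SAP 11.7 plans them by infusion rate and time point. Neither section plans a change or shift summary. The nearest item is the SAP 11.5.1 listing for subjects whose hemoglobin falls by more than 1 g/dL from the mean of the Screening and pre-IMP values.

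**The case against.** The strongest reply is that little depends on these grades. The SBI analysis (SAP 10.1), the analysis of infusions with temporally associated events (SAP 11.1) and the stopping rules (protocol 8.1) do not use the scale. Abnormal values are flagged whatever their grade. Under protocol 10.1.1 and 10.3, clinically significant laboratory findings count as AEs and are repeated and followed. Protocol 10.1.5 has its own mild, moderate and severe criteria for AEs. All of this stands, and it makes the point a minor one.

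Four stronger readings are tempting, and the documents do not support them.

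- **That children's grades will be wrong.** This is a claim about the scale's contents. Without the cut-offs, one can say only that the grades may be invalid below the titled age range.
- **That the whole pediatric cohort is affected.** At least 6 of the children must be aged 12 to <17, and they fit the title by age. The 24% to 76% counts children under 12; it is not a misgrading rate.
- **That age effects will be mistaken for drug effects.** SAP 6.1 shows the age groups separately, so an age pattern would be visible. SAP 11 sets the commercial-product and IMP periods side by side. For a child with both periods, an age artefact should appear under both.
- **That pre-existing abnormality is ignored.** Protocol 10.3 does not count findings present before the first IMP dose as AEs unless they worsen, baseline values are summarized, and the hemoglobin listing uses a baseline. What remains is that the SAP has no change or shift summary for endpoints that the protocol defines as changes.

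The title's restriction to healthy volunteers is a separate mismatch that touches patients of every age. An age limit does not cure it, although summaries against each subject's own baseline help.

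**Conclusion.** The point holds in limited form. SAP 11.5.5 and 11.7 apply the scale to children aged 2 to <12, whom its title does not cover, and graded results for them may be invalid. That is 6 to 19 of about 25 children, or 12 to 19 if the youngest stratum fills. The count assumes that Cohort 2 reaches 25, that the strata limits are kept, and that adolescence starts at 12. The extent of any misgrading is unknown. The effect is confined to descriptive safety tables, so this is a desirable improvement and not a threat to the trial's conclusions. The missing change-from-baseline summaries are a smaller, related gap between the SAP and protocol 5.2.

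**What to change.** In SAP 11.5.5 and 11.7:

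1. Limit this scale to subjects aged 12 and over.
2. For younger children, classify each laboratory value and vital sign as low, normal or high against age-specific reference ranges, and name the source of those ranges.
3. State that the normal-range flags already planned for the listings use the same age-specific ranges.
4. Add change- or shift-from-baseline summaries for laboratory values and vital signs, to match protocol 5.2. For subjects under 12, the shift is between range categories.

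The cost is SAP wording, a reference-range lookup and some extra tables; no new data are needed. The downside is that younger children get range categories instead of toxicity grades, so their tables cannot be pooled with graded results from older subjects.

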11.8. Pregnancy Tests

All pregnancy test data will be listed.

11.9. Viral Tests

Virology data will be summarized descriptively. Means, SD, median, minimum and maximum will be included for continuous results such as B19 IgG, and count and percentages will be reported for categorical results. Virology testing data will be listed with normal ranges and flags of abnormality.

11.10. Subject Diary

Subject diary data will be used to derive the following secondary efficacy endpoints:

- Episodes of fever ($\geq 100.4^{\circ}\text{C}$)

- Number of days out of work/school/kindergarten/day care or unable to perform normal daily activities due to infection
- Number of days of hospitalization due to infection
- Number of days of antibiotic use for infection prophylaxis and/or treatment

The subject diary data will be tabulated and listed.

12. SUBGROUP ANALYSIS

Subgroup analyses of the efficacy and safety endpoints may be performed based on gender.

13. PHARMACOKINETIC ANALYSIS

For all subjects in the PK sub-study, blood samples will be collected for the assessment of serum concentrations of total IgG before and after Infusion 6 (Week 15 \pm 2 days) for 21-day cycle subjects or Infusion 5 (Week 16 \pm 2 days) for 28-day cycle subjects at the following time points:

PK Time Points for Cohort 1 (adults):

- Pre-dose at 10 to 30 minutes before IMP Infusion 6 for 21-day cycle subjects or IMP Infusion 5 for 28-day cycle subjects
- 15 minutes (\pm 1 minute) after the end of the infusion
- 1 hour (\pm 5 minutes) after the end of the infusion
- 4 hours (\pm 15 minutes) after the end of the infusion
- 24 hours (\pm 1 hour) after the end of the infusion
- 7 days (\pm 1 day) after the end of the infusion
- 14 days (\pm 1 days) after the end of the infusion
- 21 days (\pm 1 days) after the end of the infusion (immediately before infusion at Infusion 7 for 21-day cycle subjects)
- 28 days (\pm 1 days) after the end of the infusion (immediately before infusion at Infusion 6 for 28-day cycle subjects)

PK Time Points for Cohort 2 (children):

- Pre-dose at 10 to 30 minutes before IMP Infusion 6 for 21-day cycle subjects or IMP Infusion 5 for 28-day cycle subjects
- 15 minutes (\pm 1 minute) after the end of the infusion
- 4 hours (\pm 15 minutes) after the end of the infusion
- 24 hours (\pm 1 hour) after the end of the infusion
- 10 days (\pm 1 day) after the end of the infusion
- 21 days (\pm 1 day) after the end of the infusion (immediately before infusion at Visit 7 for 21-day cycle subjects)
- 28 days (\pm 1 day) after the end of the infusion (immediately before infusion at Visit 6 for 28-day cycle subjects)

The actual times of sampling as recorded on the eCRF will be used in the PK analysis.

Total IgG concentration will be determined as defined in a laboratory plan. All concentrations below the lower limit of quantification (LLOQ) or missing data will be labeled as such and ignored in the PK analysis. IgG concentration will be baseline-corrected using the trough level obtained immediately prior to infusion as baseline. Baseline-corrected concentration equal or lower than 0 will not be used in the PK analysis.

The following PK parameters will be determined by non-compartmental analysis (NCA) using Phoenix® WinNonlin 7.0 (Pharsight) for each subject:

- Area under the concentration-time curve over 1 dosing interval (AUC_{0-t})
- Peak serum concentration (C_{max})
- Time to reach peak serum concentration (T_{max})
- The volume of distribution at steady-state (V_{ss})
- Mean residence time (MRT)
- Total body clearance (CL)
- Terminal half-life ($t_{1/2}$)

Additional PK parameters might be determined by compartmental analysis.

PK concentration profiles will be summarized over time in tabular and graphical formats. Arithmetic [and/or geometric] [mean/median] \pm SD concentration-time plots will be produced by cohort, and dosing frequency.

Descriptive statistics of PK parameters and concentrations will include mean, SD, percent coefficient of variation (CV%), minimum, median and maximum. When a geometric mean is presented, it will be labeled as such.

14. SCHEDULE OF ASSESSMENTS

14.1. Schedule of Assessments and Study Events for the CP Treatment Period

Visit/Infusion ^a	Baseline Variable Number of CP Infusions Depending on Evaluations in the First 15 Subjects with IMP														
	Screen ^r	CP1	CP2	CP3	CP4	CP5	CP6	CP7	CP8	CP9	CP10	CP11	CP12	CP13	Prior to IMP
Week (21-day cycle)	-3 week	0	3	6	9	12	15	18	21	24	27	30	33	36	
Week (28-day cycle) ^a	-4 week	0	4	8	12	16	20	24	28	32	36	40	44	48	
Pre-infusion:															
Medical history and prior ADRs specific to IgG treatment	X	X													X
Prior and concomitant medications	X	X	X	X	X	X	X	X	X	X	X	X	X	X	X
Review of eligibility criteria	X	X													X
Subject diary review		X	X	X	X	X	X	X	X	X	X	X	X	X	X
Vital signs	X	X	X	X	X	X	X	X	X	X	X	X	X	X	X
Physical examination ^e	X	X	X	X	X	X	X	X	X	X	X	X	X	X	X
Weight ^d	X	X	X	X	X	X	X	X	X	X	X	X	X	X	X
Urine pregnancy test ^e	X	X	X	X	X	X	X	X	X	X	X	X	X	X	X
IgG trough levels ^f	X														X
Anti-β2GPI and Anti-β2GPI-DI ^g	X	X	X		X				X						X
Viral testing ^h	X														
Retention sample for viral testing (pre-infusion) ⁱ		X													X
Pre-infusion laboratory safety assessments – general ^j	X	X	X	X	X				X				X		X

Visit/Infusion ^a	Baseline Variable Number of CP Infusions Depending on Evaluations in the First 15 Subjects with IMP														
	Screening ^r	CP1	CP2	CP3	CP4	CP5	CP6	CP7	CP8	CP9	CP10	CP11	CP12	CP13	Prior to IMP
Week (21-day cycle)	-3 week	0	3	6	9	12	15	18	21	24	27	30	33	36	
Week (28-day cycle) ^a	-4 week	0	4	8	12	16	20	24	28	32	36	40	44	48	
Pre-infusion hemolysis assessments ^q	X	X	X	X	X				X				X		X
CP infusion ^k		X	X	X	X	X	X	X	X	X	X	X	X	X	
Post-infusion															
Vital signs ^b		X	X	X	X	X	X	X	X	X	X	X	X	X	
Clinical evaluation for hemolysis & thrombosis: 1h after infusion ^l		X	X	X	X	X	X	X	X	X	X	X	X	X	
D-dimer: 3-4h after infusion ^m		X	X		X				X				X		
Retention sample for protein C & protein S: 3-4h after infusion ⁿ	X	X	X		X				X				X		
Phone calls 24 h & 72 h ^p		X	X	X	X	X	X	X	X	X	X	X	X	X	
Adverse event assessment ^o		X	X	X	X	X	X	X	X	X	X	X	X	X	

ADR = adverse drug reaction; IgG = immunoglobulin G; NAT = nucleic acid test; PCR = polymerase chain reaction.

- ^a The number of weeks on CP will depend on the timing of recruitment of the first 15 subjects to receive IMP. If safety review of the first 5 subjects is satisfactory and the staggering interval for the next 10 subjects (Schedule 2) can be reduced, the number of weeks on CP will be shorter than shown here. If recruitment of these subjects does not take place as quickly as planned, the number of weeks on CP may be longer.
- ^b Vital signs will be recorded before, during, and after the infusion at time points listed in Section 6.3.
- ^c Physical examination will focus on organs and systems known to be the target of complications in PIDD: skin, head, eyes, ear, nose, and throat (HEENT), respiratory, cardiovascular, abdominal, breasts (optional), genitourinary (optional), rectal (optional), musculoskeletal, neurologic (Section 6.4). Serious bacterial infections will be diagnosed as outlined in Section 21.1. Screening visit includes height measurement.
- ^d If at any visit after baseline, a subject's body weight has changed by 5% or more from the baseline value, the CP dose will be adjusted according to standards of care.
- ^e Female subjects of childbearing potential.
- ^f For subjects receiving IGIV at entry, baseline IgG levels are trough levels; for those receiving IGSC at entry, baseline IgG levels are steady state levels. Subjects on CP Waiting Period need two IgG trough/steady state levels of ≥ 5 mg/mL documented within 6 months prior to IMP Infusion 1.
- ^g Antibody titers for anti- β 2GPI and anti- β 2GPI-DI will be determined at Screening, before the CP infusion 1 as the baseline value, then before CP infusions 2, 4, and 8.
- ^h Viral testing includes HAV, HBV, HCV, HIV-1, HIV-2, and B19 using nucleic acid test (NAT) or preferably quantitative PCR, if available, and serology assays.
- ⁱ Viral testing includes HAV, HBV, HCV, HIV-1, HIV-2, and B19 using nucleic acid test (NAT) or preferably quantitative PCR, if available, and serology assays. Performed prior to IMP dosing at IMP Infusion 1 when subject comes off Waiting Period. Retention sample also collected prior to Infusion 1 IMP/CP baseline for all subjects.
- ^j Pre-infusion general laboratory safety tests include hematology, blood chemistry, and urinalysis. For subjects in the Waiting Period, testing will be done on samples collected before administration of the first four CP infusions (1, 2, 3, 4) and then before every fourth CP infusion (8, 12, 16, etc.) as long as the subject is in the Waiting Period.
- ^k Infusion rate is adjusted according to standard care. CP infusions will continue until the subject's first scheduled IMP infusion can occur.
- ^l Approximately 1 hour after each infusion, the Investigator will examine the subject to look for clinical signs of hemolysis and thrombosis (Section 6.12.2). Positive assessments will lead to a full work-up for hemolysis or thrombosis, as appropriate, according to the facility's standard of care.
- ^m Approximately 3-4 hours after CP infusions 1, 2, 4, 8, 12, 16 a blood sample will be drawn for measuring d-dimer levels.
- ⁿ Approximately 3-4h after CP infusions 1, 2, 4, 8, 12, 16 a retention sample will be drawn for testing of protein C and protein S in case d-dimer results after the first infusion indicate potential thrombosis or the PI determines a need for protein C and protein S testing based on his evaluation (Section 6.11). A retention sample will be drawn at Screening pre-infusion for later testing of protein C and protein S in case d-dimer results are positive after first infusion of CP.
- ^o Subjects are monitored for infusional AEs during CP infusions, for 3-4 hours after the first infusion, and for 1 hour after further infusions. Other AEs are recorded in the subject diaries and collected and reviewed at each visit (Section 10). All subjects are monitored for temporally associated AEs in the 24-hour and 72-hour phone calls from staff to the subject.
- ^p The study staff will call subjects 24 hours (+6 hours) and 72 hours (+12) after each infusion to evaluate the potential for hemolysis, thrombosis, and any other AEs. Positive answer on any of the five hemolysis questions or on any of the thrombosis questions will be reported to the PI for a decision as to whether a full work-up is necessary (Section 6.12.3).
- ^q Pre-infusion hemolysis laboratory tests will include urine hemosiderin, serum haptoglobin, plasma free hemoglobin, Coombs test (direct anti-globulin test). Pre-infusion hemolysis testing will be done for all subjects before administration of CP at infusions 1 (baseline value), 2, 3, 4 and then every fourth infusion (8, 12, 16, etc.). For all subjects, a drop of ≥ 2.0 g/dL from the pre-infusion hemoglobin level or clinical signs of hemolysis between visits will lead to a full hemolysis work-up (Section 6.9).
- ^r Screening visit will include demographics. Subjects treated with commercial IGIV or IGSC may receive their current treatment infusion either before the screening visit or at the screening visit if screening laboratory samples are taken prior to the infusion. Subjects receiving IGSC when they enter the study will have their screening visit up to 17 days prior to the Baseline Visit.

14.2. Schedule of Assessments and Study Events for the IMP Treatment Period

Visit/Infusion	Baseline		Treatment with IMP														TC ^a	LTSV ^{b,b}	
	Screen Visit ^{aa}	IMP 1 ^a	IMP 2	IMP 3	IMP 4	IMP 5	IMP 6	IMP 7	IMP 8	IMP 9	IMP 10	IMP 11	IMP 12	IMP 13 ^b	IMP 14 ^b	IMP 15 ^b			IMP 16 ^b
Week (21-day cycle)	-3 weeks	0	3	6	9	12	15	18	21	24	27	30	33	36	39	42	45	48	51
Visit/Infusion	Screen Visit ^{aa}	IMP 1 ^a	IMP 2	IMP 3	IMP 4	IMP 5	IMP 6	IMP 7	IMP 8	IMP 9	IMP 10	IMP 11	IMP 12	-	-	-	-	IMP 13 ^c	Standard 14 ^d
Week (28-day Cycle)	-4 weeks	0	4	8	12	16	20	24	28	32	36	40	44	-	-	-	-	48	52
Pre-infusion																			
Medical History and prior ADRs to IgG	X																		
Concomitant medications	X	X	X	X	X	X	X	X	X	X	X	X	X	X	X	X	X	X	X
Review eligibility criteria	X	X																	
Subject diary review		X	X	X	X	X	X	X	X	X	X	X	X	X	X	X	X	X	X
Vital signs	X	X	X	X	X	X	X	X	X	X	X	X	X	X	X	X	X	X	X
Physical examination ^e	X	X	X	X	X	X	X	X	X	X	X	X	X	X	X	X	X	X	X
Weight ^h		X	X	X	X	X	X	X	X	X	X	X	X	X	X	X	X	X	X
Urine pregnancy test ⁱ	X	X	X	X	X	X	X	X	X	X	X	X	X	X	X	X	X	X	X
IgG trough levels ^j	X	X	X	X	X	X	X	X	X	X	X	X	X	X	X	X	X	X	X
Anti-β2GPI and Anti-β2GPI-DI ^k	X	X	X		X				X										X
Retention sample for immunogenicity ^l		X	X	X	X	X	X	X	X	X	X	X	X	X	X	X	X	X	X

Visit/Infusion	Baseline		Treatment with IMP														TC ^a	LTSV ^{b,b}	
	Screen Visit ^{aa}	IMP 1 ^a	IMP 2	IMP 3	IMP 4	IMP 5	IMP 6	IMP 7	IMP 8	IMP 9	IMP 10	IMP 11	IMP 12	IMP 13 ^b	IMP 14 ^b	IMP 15 ^b			IMP 16 ^b
Week (21-day cycle)	-3 weeks	0	3	6	9	12	15	18	21	24	27	30	33	36	39	42	45	48	51
Visit/Infusion	Screen Visit ^{aa}	IMP 1 ^a	IMP 2	IMP 3	IMP 4	IMP 5	IMP 6	IMP 7	IMP 8	IMP 9	IMP 10	IMP 11	IMP 12	-	-	-	-	IMP 13 ^c	Standard 14 ^d
Week (28-day Cycle)	-4 weeks	0	4	8	12	16	20	24	28	32	36	40	44	-	-	-	-	48	52
Viral testing ^{ma}	X	X ^a			X ^m	X ^m													X
Retention sample for viral testing ⁿ		X																	X
Pre-infusion laboratory safety assessments ⁿ	X	X	X	X	X				X				X				X	X	X
Pre-infusion hemolysis assessments ^{o,p}	X	X	X	X	X				X				X				X	X	X
IMP infusion ^q		X ^o	X ^o	X ^p	X ^p	X ^p	X ^p	X ^p	X ^p	X ^p	X ^p	X ^p	X ^p	X ^p	X ^p	X ^p	X ^p	X ^p	
Post-infusion																			
Vital signs ^r		X	X	X	X	X	X	X	X	X	X	X	X	X	X	X	X	X	X
Clinical evaluation for hemolysis & thrombosis: 1 h post infusion ^q		X	X	X	X	X	X	X	X	X	X	X	X	X	X	X	X	X	
D-dimer: 3-4 h post-infusion ^r		X ^r	X		X				X				X					X	
Retention sample for protein C & protein S: 3-4 h post-infusion ^r	X	X ^r	X		X				X				X					X	
Phone calls 24 h & 72 h ^s		X	X	X	X	X	X	X	X	X	X	X	X	X	X	X	X	X	

Visit/Infusion	Baseline		Treatment with IMP														TC ^a	LTSV ^{bb} Standard 18 ^d	
	Screen Visit ^{aa}	IMP 1 ^c	IMP 2	IMP 3	IMP 4	IMP 5	IMP 6	IMP 7	IMP 8	IMP 9	IMP 10	IMP 11	IMP 12	IMP 13 ^b	IMP 14 ^b	IMP 15 ^b			IMP 16 ^b
Week (21-day cycle)	-3 weeks	0	3	6	9	12	15	18	21	24	27	30	33	36	39	42	45	48	51
Visit/Infusion	Screen Visit ^{aa}	IMP 1 ^c	IMP 2	IMP 3	IMP 4	IMP 5	IMP 6	IMP 7	IMP 8	IMP 9	IMP 10	IMP 11	IMP 12	-	-	-	-	IMP 13 ^c	Standard 14 ^d
Week (28-day Cycle)	-4 weeks	0	4	8	12	16	20	24	28	32	36	40	44	-	-	-	-	48	52
7-day post-infusion lab safety assessments – general ^u		X	X		X				X				X					X	
2-3 day and 7-day post-infusion lab safety assessments—hemolysis ^v		X	X		X				X ^y				X ^y					X ^y	
PK sub-study						X ^w	X ^w												
Adverse event assessment ^z		X ^z	X	X	X	X	X	X	X	X	X	X	X	X	X	X	X	X	X

ADR = adverse drug reaction; IgG = immunoglobulin G; LTSV = long-term safety visit; LTSF = long-term safety follow-up; NAT = nucleic acid test; PCR = polymerase chain reaction; PK = pharmacokinetics; TC = treatment completion or termination visit.

- ^a For subjects who terminate the study before the planned treatment completion visit, all procedures should be performed at the final scheduled visit. If a subject is terminating early and will be unable to return for the LTSV visit, additional procedures for LTSV (safety laboratory test, viral testing, and retention sample) must also be performed at the final visit.
- ^b 21-day cycle only
- ^c Subjects on the 21-day cycle will receive 17 infusions of the IMP, and subjects on the 28-day cycle will receive 13 infusions of the IMP in one year.
- ^d Subjects resume standard IgG treatment.
- ^e Viral testing includes HAV, HBV, HCV, HIV-1, HIV-2, and B19 using nucleic acid test (NAT) or preferably quantitative PCR, if available, and serology assays. Subjects coming off of Waiting Period must have viral testing prior to IMP Infusion 1.
- ^f Vital signs will be recorded before, during, and after the IMP infusion at time points listed in Section 6.3. At the LTSV, vital signs will be recorded before administration of the subject's standard immunoglobulin treatment, but no post-infusion measurement is required.
- ^g Physical examination will focus on organs and systems known to be the target of complications in PIDD: skin; head, eyes, ear, nose, and throat (HEENT); respiratory, cardiovascular, abdominal, breasts (optional), genitourinary (optional), rectal (optional), musculoskeletal, neurologic (Section 6.4). Serious bacterial infections will be diagnosed as outlined in Section 21.1. A chest X-ray will be performed between the Screening visit and the IMP Infusion 1, unless a chest X-ray has been performed within 6 months prior to the first study infusion (CP or IMP) and demonstrates a normal result. Screening visit includes height measurement.
- ^h If at any visit after baseline, a subject's body weight has changed by 5% or more from the baseline value, the IMP dose will be adjusted accordingly (Section 13.6.1).
- ⁱ Female subjects of childbearing potential.
- ^j For subjects receiving IGIV at study entry, IgG levels are trough levels; for those receiving IGSC at study entry, baseline IgG levels are steady state levels. Subjects (including those coming off of the CP Waiting Period) need two IgG trough/steady state levels of ≥ 5 mg/ mL documented within 6 months prior to IMP Infusion 1.
- ^k Antibody titers for anti- β 2GPI and anti- β 2GPI-DI, will be done at Screening, before IMP infusion 1 as the baseline value, then before infusions 2, 4, and 8, and at the LTSV.
- ^l Retention samples for anti- β 2GPI and anti- β 2GPI-DI antibodies will be taken at every infusion visit.
- ^m Interim viral testing will be performed at Week 12 (IMP Infusion 5 for subjects on the 21-day cycle; IMP Infusion 4 for subjects on the 28-day cycle). Retention sample also collected prior to Infusion 1 IMP/CP baseline for all subjects. Final viral testing will be performed at the LTSV (Section 6.7).
- ⁿ Pre-infusion general laboratory safety tests include general safety (hematology, blood chemistry, and urinalysis) (Section 6.8).
- ^o Infusion rate is adjusted every 30 minutes based on tolerability as described in Section 13.6.2.1.
- ^p Infusion rate is adjusted every 15 minutes based on tolerability as described in Section 13.6.2.2.
- ^q Approximately 1 hour after each infusion, the Investigator will examine the subject to look for clinical signs of hemolysis and thrombosis (Section 6.12.2). Positive assessments will lead to a full work-up for hemolysis (Section 6.12) or thrombosis, as appropriate, according to the facility's standard of care.
- ^r Approximately 3-4 hours after the first IMP infusion (IMP baseline), a blood sample will be drawn for measuring d-dimer levels, and a retention sample will also be drawn for testing of protein C and protein S in case d-dimer results indicate potential thrombosis or the PI determines a need for protein C and protein S testing based on his evaluation (Section 6.11). A retention sample will be drawn at Screening pre-infusion for later testing of protein C and protein S in case d-dimer results are positive after the first infusion of IMP.
- ^s The study staff will call subjects 24 hours (+6 hours) and 72 hours (+12 hours) after each infusion to evaluate the potential for hemolysis, thrombosis, and any other AEs. Positive answer on any of the five hemolysis questions or on any of the thrombosis questions will be reported to the PI for a decision as to whether a full work-up is necessary (Section 6.12.3).
- ^t Post-infusion general laboratory safety tests will include hematology, blood chemistry, and urinalysis (Section 6.8). For Groups 1 and 2, post-infusion general safety laboratory testing will be done while receiving IMP, 7 days (± 1 day) after IMP Infusions 1, 2, and 4, and then 7 days (± 1 day) after every fourth infusion (8, 12, 16). For Group 3, post-infusion general safety laboratory testing will be done while receiving IMP, 7 days (± 1 day) after IMP Infusions 1 and 4.

- ^v Post-infusion hemolysis laboratory tests will include urine hemosiderin, serum haptoglobin, plasma free hemoglobin, Coombs test (direct anti-globulin test) (Section 6.9). For Groups 1 and 2, post-infusion hemolysis testing will be done while receiving IMP, 2-3 days and again 7 days (± 1 day) after IMP Infusions 1, 2, and 4, and then 7 days (± 1 day) after every fourth infusion (8, 12, 16). For Group 3, post-infusion hemolysis testing will be done while receiving IMP, 7 days (± 1 day) after IMP Infusions 1 and 4.
- ^w Subjects who participate in the PK sub-study will have blood samples drawn before and after IMP Infusion 6 (21-day cycle subjects) or IMP Infusion 5 (28-day cycle subjects) at time points listed in Section 6.13.
- ^x Subjects are monitored for infusion-related AEs during the IMP infusions, for 3-4 hours after the first infusion, and for 1 hour after further infusions. Other AEs are recorded in the subject diaries and collected and reviewed at each visit (Section 10). All subjects are monitored for temporally associated AEs in the 24-hour and 72-hour phone calls from staff to the subject as described above.
- ^y Pre-infusion hemolysis laboratory tests will include urine hemosiderin, serum haptoglobin, plasma free hemoglobin, Coombs test (direct anti-globulin test) (Section 6.9). Pre-infusion hemolysis testing will be done for all subjects before administration of IMP at infusions 1 (baseline value), 2, 3, 4 and every fourth infusion (8, 12, 16), TCTV and at the LTSV. For all subjects, a drop of ≥ 2.0 g/dL from the pre-infusion hemoglobin level or clinical signs of hemolysis between visits will lead to a full hemolysis work-up (Section 6.9)
- ^z All subject groups will have pre-infusion hemolysis testing prior to IMP/CP infusion 1. For all subjects, a drop of ≥ 2.0 g/dL from the pre-infusion hemoglobin level or clinical signs of hemolysis between visits will lead to a full hemolysis work-up (Section 6.9)
- ^{aa} Screening visit will include demographics. Subjects treated with commercial IGIV or IGSC may receive their current treatment infusion either before the screening visit or at the screening visit if screening laboratory samples are taken prior to the infusion. Subjects receiving IGSC when they enter the study will have their screening visit up to 17 days prior to the Baseline Visit.
- ^{bb} For subjects who discontinue IMP due to events (hemolysis, thrombosis, anti- $\beta 2$ GPI immunogenicity), and for all subjects if study is stopped, follow-up LTSF will continue for additional cycles (Section 7.11). For subjects who discontinue IMP due to anti- $\beta 2$ GPI immunogenicity, subject will continue to be followed up and have the LTSF performed until immunogenicity titers are stabilized (or dropping) over 3 consecutive treatment cycles (21-day cycle/ 28-day cycle). (Section 7.11)

